6.1. Inclusion Criteria

Patients are eligible to be included in the study only if they meet all of the following criteria at screening:

Type of Patient and Disease Characteristics

[1] Have been diagnosed with T2DM based on the World Health Organization classification or other locally applicable diagnostic standards and have been treated with insulin glargine (U100), once daily with or without metformin ≥3 months prior to Visit 1

Patient Characteristics

- [2] Have HbA1c ≥7.0% (53 mmol/mol) to ≤10.5% (91 mmol/mol), as determined by the central laboratory at Visit 1
- [3] Have been on stable doses of once-daily insulin glargine (>0.25 U/kg/day or >20 U/day) and metformin (if taken) during the 3-month period prior to Visit 1. Insulin glargine dose is considered stable when all doses during this period are within the range defined by ±20% of the most commonly used insulin dose during this same period. Doses of metformin are considered stable if all prescribed doses during this period are in the range between the minimum required dose (≥1500 mg/day) and the maximum approved dose per the locally approved label
- [4] Require further insulin glargine dose increase at Visit 3 per the TTT algorithm based on the SMBG data collected during the prior week
- [5] Are of stable weight (±5%) ≥3 months prior to Visit 1 and agree to not initiate a diet and/or exercise program during the study with the intent of reducing body weight other than the lifestyle and dietary measures for diabetes treatment
- [6] Have body mass index (BMI) ≥23 kg/m² at Visit 1
- [7] Are 18 years old or of an acceptable age to provide informed consent according to local regulations, whichever is older
 - (a) Male patients:
 - Male patients should be willing to use reliable contraceptive methods throughout the study and for at least 3 months after last injection (Appendix 6)
 - (b) Female patients:

- Female patients not of childbearing potential due to surgical sterilization (hysterectomy or bilateral oophorectomy or tubal ligation), congenital anomaly (i.e., Mullerian agenesis) or menopause.
 - Women with an intact uterus are deemed postmenopausal if they are 45 years old, and
 - have not taken hormones or oral contraceptives within the last year and had cessation of menses for at least 1 year,

OR

- have had at least 6 months and less than 12 months of spontaneous amenorrhea with follicle-stimulating hormone (FSH) and estradiol levels consistent with a postmenopausal state (FSH ≥40 mIU/mL and estradiol <30 pg/mL).
- Female patients of childbearing potential (not surgically sterilized and between menarche and 1-year postmenopausal) must:
 - test negative for pregnancy at Visit 1 based on a serum pregnancy test

AND

- if sexually active, agree to use 2 forms of effective contraception, where at least one form is highly effective for the duration of the trial and for 30 days thereafter
- not be breastfeeding
- [8] In the investigator's opinion, are well-motivated, capable, and willing to:
 - (a) perform fingerstick BG monitoring, including scheduled BG profiles with up to 7 measurements in 1 day
 - (b) learn how to self-inject study drugs as required for this protocol (visually impaired persons who are not able to perform the injections must have the assistance of a sighted individual trained to inject the study drug; persons with physical limitations who are not able to perform the injections must have the assistance of an individual trained to inject the study drug)
 - (c) are willing and able to inject study drugs
 - (d) maintain a study diary, as required for this protocol
 - (e) have a sufficient understanding of one of the provided languages of the country such that they will be able to complete the patient questionnaires

Informed Consent

[9] Have given written informed consent to participate in this study in accordance with local regulations and the ethical review board (ERB) governing the study site

6.2. Exclusion Criteria

Patients will be excluded from study enrollment if they meet any of the following criteria at screening:

Medical Conditions

- [10] Have type 1 diabetes mellitus (T1DM)
- [11] Had chronic or acute pancreatitis any time prior to study entry (Visit 1)
- [12] Have history of:
 - proliferative diabetic retinopathy

or

• diabetic maculopathy

or

• nonproliferative diabetic retinopathy that requires acute treatment

(a dilated fundoscopic examination performed by an ophthalmologist or optometrist between Visit 2 and Visit 3 is required to confirm eligibility)

- [13] Have a history of severe hypoglycemia and/or hypoglycemia unawareness within the 6 months prior to Visit 1
- [14] Have a history of diabetic ketoacidosis or hyperosmolar state/coma
- [15] Have a known clinically significant gastric emptying abnormality (for example, severe diabetic gastroparesis or gastric outlet obstruction), have undergone or plan to have during the course of the study: a gastric bypass (bariatric) surgery or restrictive bariatric surgery (for example, Lap-Band®), or chronically take drugs that directly affect GI motility
- [16] Have any of the following cardiovascular (CV) conditions within 2 months prior to Visit 1: acute myocardial infarction, or cerebrovascular accident (stroke) or hospitalization due to congestive heart failure (CHF)
- [17] Have New York Heart Association Functional Classification III and IV CHF
- [18] Have acute or chronic hepatitis, signs and symptoms of any other liver disease other than nonalcoholic fatty liver disease (NAFLD), or alanine aminotransferase (ALT) level >3.0 times the upper limit of the reference range, as determined by the central laboratory at study entry; patients with NAFLD are eligible for participation in this trial only if their ALT level is ≤3.0 times the upper limit of normal (ULN) for the reference range
- [19] Have an estimated glomerular filtration rate <30 mL/min/1.73 m², calculated by Chronic Kidney Disease-Epidemiology as determined by central laboratory at Visit 1; for patients on metformin, estimated glomerular filtration rate <45 mL/min/1.73 m² (or lower than the country-specific threshold for using the protocol-required dose of metformin per local label)

- [20] Have evidence of a significant, uncontrolled endocrine abnormality (for example, thyrotoxicosis or adrenal crises), in the opinion of the investigator
- [21] Have family or personal history of medullary thyroid carcinoma (MTC) or multiple endocrine neoplasia syndrome type 2
- [22] Have a serum calcitonin level of ≥35 ng/L, as determined by central laboratory at Visit 1
- [23] Known or suspected hypersensitivity to trial product(s) or related products
- [24] Have evidence of a significant, active autoimmune abnormality (for example, lupus or rheumatoid arthritis) that, in the opinion of the investigator, is likely to require concurrent treatment with systemic glucocorticoids in the next 12 months
- [25] Have had a transplanted organ (corneal transplants [keratoplasty] allowed) or awaiting an organ transplant
- [26] Have a history of an active or untreated malignancy or are in remission from a clinically significant malignancy (other than basal or squamous cell skin cancer, in situ carcinomas of the cervix, or in situ prostate cancer) for less than 5 years
- [27] Have a history of any other condition (such as known drug, alcohol abuse, or psychiatric disorder) that, in the opinion of the investigator, may preclude the patient from following and completing the protocol
- [28] Have any hematological condition that may interfere with HbA1c measurement (for example, hemolytic anemias and sickle cell disease)

Prior/Concomitant Therapy

- [29] Treatment with any glucose-lowering agent(s) other than stated in the inclusion criteria [4] in a period of 3 months prior to Visit 1 and between Visit 1 and Visit 3
- [30] Have been treated with prescription drugs that promote weight loss (for example, Saxenda [liraglutide 3.0 mg], Xenical[®] [orlistat], Meridia[®] [sibutramine], Acutrim[®] [phenylpropanolamine], Sanorex[®] [mazindol], Apidex[®] [phentermine], BELVIQ[®] [lorcaserin], Qsymia[™] [phentermine/topiramate combination], Contrave[®] [naltrexone/bupropion], or similar other body weight loss medications including over-the-counter (OTC) medications [for example, allī[®]]) within 3 months prior to Visit 1 and/or between study entry (Visit 1) and randomization (Visit 3)
- [31] Are receiving chronic (>2 weeks or 14 days) systemic glucocorticoid therapy (excluding topical, intraocular, intranasal, or inhaled preparations) or have received such therapy within 1 month of Visit 1 or between Visits 1 and 3

Prior/Concurrent Clinical Trial Experience

[32] Are currently enrolled in any other clinical study involving an investigational product or any other type of medical research judged not to be scientifically or

- medically compatible with this study
- [33] Have participated, within the last 30 days in a clinical study involving an investigational product. If the previous investigational product has a long half-life, 5 half-lives or 30 days (whichever is longer) should have passed
- [34] Have previously completed or withdrawn from this study or any other study investigating tirzepatide

Other Exclusions

- [35] Are investigator site personnel directly affiliated with this study and/or their immediate families. Immediate family is defined as a spouse, parent, child, or sibling, whether biological or legally adopted
- [36] Are Lilly employees
- [37] Are unwilling or unable to comply with the use of a paper diary to directly record data from the subject

6.3. Lifestyle Restrictions

Per the Schedule of Activities (Section 2), qualified medical staff will provide diabetes management counseling, which will include instructions on diet and exercise and education about the signs, symptoms, and treatment of hypoglycemia, should it occur.

Patients should continue their usual exercise habits and generally follow a healthy meal plan (with consistent meal size and time of day) throughout the course of the study. Dietary counseling may be reviewed throughout the study, as needed. Per inclusion criterion [5] (Section 6), patients should not initiate during the study an organized diet and/or exercise weight reduction program other than the lifestyle and dietary measures for diabetes treatment.

Study participants should be instructed not to donate blood or blood products during the study.

6.4. Screen Failures

Individuals who do not meet the criteria for participation in this study (screen failure) must not be rescreened.

7. Treatments

7.1. Treatments Administered

Eligibility for this study will be determined at the initial screening visit (Visit 1). Screening procedures and patient training will be performed at Visits 1 and 2 (screening and lead-in periods). Patient training will include disease monitoring and management procedures, study diaries, and study procedures. At Visit 3, patients will perform all required baseline study procedures (including the collection of all baseline laboratory measures and ECG) prior to randomization and prior to taking the first dose of study drug. Following randomization, the patient will inject the first dose of study drug/placebo at the study site. The date and time of all doses of study drug should be recorded on the electronic case report form (eCRF). Beginning at randomization, all patients will receive study drug according to the randomized treatment group for the duration of the 40-week treatment period. A safety follow-up visit will occur approximately 4 weeks following the last dose of the study drug.

7.1.1. Tirzepatide Dosing

The starting dose of tirzepatide will be 2.5 mg once weekly for 4 weeks, followed by an increase to 5 mg once weekly, for the duration of the study in the 5-mg group. For the 10-mg group, the starting dose of tirzepatide will be 2.5 mg once weekly for 4 weeks, then the dose will be increased by 2.5 mg every 4 weeks (2.5 to 5 to 7.5 to 10 mg) until the 10-mg dose is reached and maintained for the duration of the study. For the 15-mg group, the starting dose of tirzepatide will be 2.5 mg once weekly for 4 weeks, then the dose will be increased by 2.5 mg every 4 weeks (2.5 to 5 to 7.5 to 10 to 12.5 to 15 mg) until the 15-mg dose is reached and maintained for the duration of the study.

7.1.2. Placebo Dosing

Patients randomized to the placebo group will inject matched placebo subcutaneously QW for the entire treatment period. This is a double-blind study, and therefore it will not be possible for investigators and patients to know which treatment they are receiving.

7.1.3. Insulin Glargine Dosing

Insulin glargine will be injected once daily, as a single SC injection, always at the same time of day, ideally at bedtime. Patients will be instructed to adjust insulin glargine doses to a target FBG of <100 mg/dL (5.5 mmol/L) according to the schedule below (Table GPGI.3). For this purpose, patients will be required to measure their FBG each morning and to collect 4-point SMBG profiles at least once a week. The 4-point SMBG profile will consist of fasting, premidday meal, pre-evening meal, and bedtime measures. Patients will collect the 4-point SMBG profiles once weekly between Visit 2 and Visit 3, twice weekly from Visits 3-7 (Weeks 0-4) followed by once weekly for the remainder of the study.

Median Fasting Blood Glucose ^a		Adjustment of Insulin Glargine if	Adjustment of Insulin Glargine if
mg/dL	mmol/L	Dose is <20 Units	Dose is ≥20 Units
≤70	≤3.9	−1 or −2 units ^{b,c}	−2 to 4 units ^{b,c}
71 to 100	4.0 to 5.5	No adjustment	No adjustment
101 to 119	5.6 to 6.6	+1 units	+2 units
120 to 139	6.7 to 7.7	+2 units	+4 units
140 to 179	7.8 to 9.9	+3 units	+6 units
≥180	≥10.0	+4 units	+8 units

Table GPGI.3. Treat-to-Target Algorithm

Abbreviation: SMBG = self-monitored blood glucose.

- a Based on the last 3 SMBG values.
- b Dose should also be decreased by 1 to 2 units or 2 to 4 units in the following situations: If multiple episodes of nonsevere hypoglycemia were recorded during the assessment period at any time during the day, and/or
 - If at least 1 episode that met the criteria for severe hypoglycemia (events requiring assistance of a third person to administer therapy) or was associated with SMBG value <54 mg/dL (<3.0 mmol/L) was recorded during the assessment period.
- c If only 1 hypoglycemic episode with SMBG value ≥54 mg/dL (≥3.0 mmol/L) and ≤70 mg/dL (≤3.9 mmol/L) was recorded, insulin dose should not be changed.

Source: Adapted from Riddle et al. 2003.

The site personnel will instruct the patient, with the patient insulin dose adjustment from the patient diary and study-specific training materials provided to the study sites, when and how to assess whether an insulin dose adjustment is needed using the algorithm. The investigator or his or her designee is responsible to ensure that the insulin dose titration regimen used by study participants follows the same requirements defined in the TTT plan throughout the study. The patient is responsible for completing the insulin dose assessments and making the required dose adjustments (self-adjustment). Assessment of insulin doses per the TTT algorithm and administered insulin doses will be recorded by the patient in study period-specific diaries. Patients should be instructed to contact the study site if they are unable to decide on the appropriate dose adjustment at any time during the trial. Site personnel will verify at each office or telephone visit that the assessment(s) has been made and that the insulin adjustment was appropriate. If needed, they will propose further adjustments based upon their review of data collected since the previous visit. If assessments were not made or the algorithm was not correctly followed, patients will receive additional training and instructions.

During the lead-in period (Visits 2 and 3 [baseline]), insulin doses should be adjusted per TTT algorithm (Table GPGI.3) only when needed to protect the safety of patients (occurrence of hypoglycemia or severe persistent hyperglycemia). See Section 5.1 for more details. Insulin dose assessments during this period will occur once per week.

During the treatment period, office visits will occur weekly or every other week during the first 2 months, and thereafter every 4 to 8 weeks to enable the site to properly monitor patients' usage of the TTT algorithm. After randomization, during the 4-week stabilization period, the insulin

glargine dose will remain unchanged if the patient's baseline (Visit 3) HbA1c is >8.0%. For patients with baseline HbA1c ≤8.0%, the insulin glargine dose will be decreased by 20% immediately (within 7 days) after randomization and will then remain unchanged during the stabilization period. Additional insulin dose adjustments during the stabilization period will only be allowed using the TTT algorithm (Table GPGI.3) in case of the occurrence of hypoglycemia or the development of severe hyperglycemia. See Section 5.1 for more details. Patients will be requested to perform insulin dose assessments twice per week during the stabilization period for safety purposes. Following stabilization, patients will be treated for an additional 36 weeks, and they will be required to assess their insulin glargine dose once weekly, using the FBG values for that week. During this period, the insulin dose will be adjusted per the TTT algorithm as described in Section 5.1 with no restriction. The decision to adjust insulin glargine doses will be based upon the median of the last 3 daily FBG (SMBG) values collected after the previous dose assessment. If only 2 values are available for assessment, then the average value will be calculated and used to adjust the dose. If only one value is available, the patient should contact the investigator site for instructions on adjusting insulin dose. In case of recorded hypoglycemic episodes any time during the period included in the assessment, the criteria provided in Table GPGI.3 should be followed.

Patients will be permitted to use concomitant medications that they require during the study, except certain medications that may interfere with the assessment of efficacy and safety characteristics of the study treatments. Antihyperglycemic medications other than study drugs are not allowed at any time during the study except as allowed for rescue therapy, and after early study drug discontinuation. Rescue therapy with other glucose-lowering agents, including prandial insulin, may be medically indicated in certain situations after randomization due to severe, persistent hyperglycemia or early discontinuation of study treatment. Rescue treatment with GLP-1 receptor agonists, pramlintide, DPP-4 inhibitors or other basal insulins will not be allowed. Short-term treatment with a nonstudy insulin for less than 14 days is allowed for certain clinical situations (for example, elective surgery, during hospitalization, hyperosmolar states). If insulin is prescribed as a rescue therapy, it must be differentiated from short-term use of insulin therapy for medical emergencies when reported in the eCRF.

All nonstudy medications will be recorded on source documents at all visits.

Nonstudy medications taken by patients who are screened, but not randomized will not be reported to Lilly unless a SAE or AE occurs that the investigator believes may have been caused by a study procedure.

7.1.4. Packaging and Labelling

The sponsor will provide tirzepatide and placebo in SDPs. These will be dispensed via an interactive web-response system (IWRS). Single-dose pens will be packaged in cartons to be dispensed. Clinical study materials will be labeled according to the country's regulatory requirements.

7.1.5. Medical Devices

The combination products used in the study are tirzepatide investigational SDP and a marketed insulin glargine prefilled pen.

7.2. Method of Treatment Assignment

Patients who meet all criteria for enrollment will be randomized to one of the study treatment groups at Visit 3. Assignment to treatment groups will be determined by a computer-generated random sequence using an IWRS. Patients will be randomized in a 1:1:1:1 ratio to receive tirzepatide 5 mg, 10 mg, 15 mg, or placebo.

7.2.1. Selection and Timing of Doses of Study Drug

Assignment to tirzepatide (3 doses) or placebo will occur at randomization.

There are no restrictions on the time of day each weekly dose of study drug is given, but it is advisable to administer the SC injections on the same day and same time each week. The actual date and time of all dose administrations will be recorded by the patient. If a dose of study drug is missed, the patient should take it as soon as possible unless it is within 72 hours of the next scheduled dose, in which case, that dose should be skipped and the next dose should be taken at the appropriate time.

All patients will inject study drug subcutaneously in the abdomen or thigh using the SDP; a caregiver may administer the injection in the patient's upper arm. A new SDP will be used for each injection. If study drug is to always be injected in the same body region, patients should be advised to use a different injection site each week.

7.3. Blinding

This is a double-blind study.

To preserve the blinding of the study, a minimum number of Lilly personnel will see the randomization table and treatment assignments before the study is complete.

Emergency codes, generated by a computer drug-labeling system, will be available to the investigator. These codes, which reveal the patient's treatment group when opened, may be opened during the study ONLY if the patient's well-being requires knowledge of the patient's treatment assignment.

Emergency unblinding for AEs may be performed through the IWRS, which may supplement or take the place of emergency codes generated by a computer drug-labeling system. This option may be used ONLY if the patient's well-being requires knowledge of the patient's treatment assignment. All calls resulting in an unblinding event are recorded and reported by the IWRS.

If an investigator, site personnel performing assessments, or patient is unblinded, the patient must be discontinued from the study. In cases where there are ethical reasons to have the patient remain in the study, the investigator must obtain specific approval from a Lilly clinical research physician (CRP) for the patient to continue in the study.

In case of an emergency, the investigator has the sole responsibility for determining if unblinding of a patient's treatment assignment is warranted for medical management of the event. The patient safety must always be the first consideration in making such a determination. If a patient's treatment assignment is unblinded, Lilly must be notified immediately. If the investigator decides that unblinding is warranted, it is the responsibility of the investigator to promptly document the decision and rationale and notify Lilly as soon as possible.

7.4. Dosage Modification

7.4.1. Study Drugs

No adjustment in study drug doses will be allowed. Details about dose administration of tirzepatide during the study are described in Section 7.1.

7.4.2. Reduction and/or Discontinuation of Concomitant Antihyperglycemic Medications

- If increased risk of hypoglycemia during the period between 2 insulin dose assessments is judged to be related to the treatment regimen, the following changes should be made:
 - Decrease the insulin glargine dose by 2 to 4 U, per the TTT algorithm, in the following cases:
 - If the median FPG value for the assessment period is ≤70 mg/dL (≤3.9 mmol/L); and/or
 - If multiple episodes of nonsevere hypoglycemia were recorded at any time during the day for the assessment period; and/or
 - If at least 1 episode that met the criteria for severe hypoglycemia (events requiring assistance to administer therapy) or was associated with SMBG value <54 mg/dL (<3.0 mmol/L) was recorded during the assessment period;
 - In the case of repeated hypoglycemic events, even with a very low glargine dose and despite glargine dose decreases per the TTT algorithm, administration of insulin glargine may be temporarily or permanently discontinued;
 - If increased risk of hypoglycemia persists despite discontinuation of insulin glargine, then dose reduction or discontinuation of metformin (for patients who are taking it) should be considered.
- 2) In certain situations short-term discontinuation will be required in line with the product(s) labeling for each respective country (for example, for metformin: severe dehydration, elective surgery, or need for radiologic examination involving IV iodinated contrast dye). Once the situation that led to temporary discontinuation of the drug resolved, treatment should be restarted at investigator discretion.

3) If a patient develops contraindications to metformin (if used), such that the use of the drug is contraindicated according to the country-specific label, the drug should be discontinued; in this case, the insulin glargine dose may need to be further adjusted.

A patient will be considered noncompliant with the protocol (protocol deviation) if he or she changes the dose or discontinues metformin (if used) for reasons other than those described here. In the case of noncompliance that lasts >14 days during the treatment period, the patient will not be included in the per-protocol analyses.

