the treatment period. Discontinuation of metformin or changes in its dose will not be permitted, except in the cases of development of contraindications (per country-specific label) for its use or in the case of increased risk of hypoglycemia (see Section 7.4.2 for details).

The starting dose of tirzepatide will be 2.5 mg QW for 4 weeks, followed by an increase to 5 mg QW, for the duration of the study in the 5 mg group. For the 10 mg group, the starting dose of tirzepatide will be 2.5 mg QW for 4 weeks, then the dose will be increased by 2.5 mg every 4 weeks (2.5 to 5 to 7.5 to 10 mg) until the 10 mg dose is reached and maintained for the duration of the study. For the 15 mg group, the starting dose of tirzepatide will be 2.5 mg QW for 4 weeks, then the dose will be increased by 2.5 mg every 4 weeks (2.5 to 5 to 7.5 to 10 to 12.5 to 15 mg) until the 15-mg dose is reached and maintained for the duration of the study. For the placebo group, patients will inject matched QW placebo for the duration of the study.

Post randomization period (end of Visit 3 to Visit 22):

Stabilization Period (End of Visit 3 through Visit 7 [Weeks 0 through 4])

The main purposes of this period are to introduce randomized study drugs (QW tirzepatide or QW placebo) in a safe manner, to assure regular and correct use of the self-monitoring and insulin dose adjustment procedures, and to study diaries during the entire study. Patients will be required to perform 4-point SMBG profiles and insulin dose assessment per the TTT algorithm twice weekly during this period. In an effort to allow appropriate time for tirzepatide to reach steady state, insulin glargine dose adjustments during the 4-week stabilization period should be restricted to those needed in the case of significant safety risks due to inadequate insulin dose:

- occurrence of hypoglycemia; (see Sections 7.4.2 and 9.2.2.1); in this case, the insulin glargine dose will be decreased per the TTT algorithm; or
- development of severe hyperglycemia, defined as mean daily PG from 4-point SMBG profile >270 mg/dL (>15 mmol/L); in this case, insulin dose will be increased per the TTT algorithm.

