Patients should be instructed to contact the sites if any of the above situations occurred, in order to adjust the insulin glargine dose per the TTT algorithm. In addition, for patients with baseline HbA1c ≤8.0%, the insulin glargine dose will be decreased by 20% immediately after randomization, not later than 7 days after the first dose of study drug, and will then remain unchanged during the stabilization period to decrease the risk of hypoglycemia. The insulin glargine dose will remain unchanged if baseline HbA1c is >8.0%. If the baseline HbA1c value for a patient is not available within the first 7 days after randomization, the study site should immediately consult the responsible Lilly physician (not later than the date of Visit 4) to discuss if an adjustment in insulin dose would be appropriate based on the available clinical data for the patient.

In addition to the clinic visits, one telephone visit will be scheduled during this period (Visit 6, Week 3). At this visit, procedures will include

- assessments of SMBG,
- adjustment of insulin dose for safety reasons (hypoglycemia and/or severe hyperglycemia),
- study drug compliance (will be re-assessed at the office visit),
- hypoglycemic events,
- concomitant medications, and
- AEs.

The data obtained at these telephone visits will be entered into the case report forms (CRFs) at the next office visit.

Titration Period (End of Visit 7 through Visit 22 [Weeks 5 through 40])

Throughout the treatment period, patients will collect the following data in the patient diary to be reviewed at the next office visit:

- SMBG.
- insulin dose assessments,
- insulin doses administered,
- dates when study drug was administered, and
- hypoglycemic events.

For that purpose, at each visit, study diaries for the period after the previous office visit, will be collected, and instructions will be reviewed at each visit. Study drug and injection supplies will be returned per the Schedule of Activities (Section 2) and according to local requirements. New supplies will be dispensed as needed.

In addition to the clinic visits, 3 telephone visits will be scheduled during this period. At each of these visits, procedures will include

- assessments of SMBG,
- compliance with insulin titration algorithm,
- insulin dose,
- study drug compliance (will be re-assessed at the office visit),
- hypoglycemic events.
- concomitant medications, and
- AEs.

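### Protocol Section 7.4.2 gives a 2 to 4 U glargine decrease for hypoglycemia at any dose, but the algorithm it cites gives 1 to 2 U below 20 U

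*Protocol*

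**What the plan says.** Section 7.4.2 applies when increased hypoglycemia risk between two insulin dose assessments is judged to come from the treatment regimen. It says: "Decrease the insulin glargine dose by 2 to 4 U, per the TTT algorithm, in the following cases". Three cases follow: a median fasting value of 70 mg/dL or less; multiple nonsevere episodes; or at least one episode that was severe or had a glucose value below 54 mg/dL. The current dose is not mentioned.

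Table GPGI.3 (Section 7.1.3) is the TTT algorithm. Its row for a median of 70 mg/dL or less gives a decrease of 1 or 2 U for doses below 20 U and 2 to 4 U for doses of 20 U or more. Footnote b extends the same two ranges to the episode-based cases: "Dose should also be decreased by 1 to 2 units or 2 to 4 units in the following situations".

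On which text governs, Section 7.1.3 says of recorded hypoglycemic episodes that "the criteria provided in Table GPGI.3 should be followed". Section 5.1, describing the stabilization period, sends the reader to 7.4.2 and also names the algorithm: "occurrence of hypoglycemia; (see Sections 7.4.2 and 9.2.2.1); in this case, the insulin glargine dose will be decreased per the TTT algorithm".

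**The concern.** Section 7.4.2 presents 2 to 4 U as the algorithm's value, and nothing in its wording tells the reader that a smaller range exists. Because Section 5.1 points sites to 7.4.2 for hypoglycemia, it is an operative reference and not background text.

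Two things are at stake. First, a patient on a low dose could have glargine cut by more than the algorithm permits. Second, compliance could be judged inconsistently. Adherence to the algorithm is recorded in the eCRF (Protocol Section 2, Schedule of Activities, footnote m) and summarized under SAP Section 6.10.1. A site that takes 3 or 4 U from 7.4.2 at a dose below 20 U follows one protocol section while departing from the table against which it is assessed.

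**Working it through.** **Step 1. Compare the two rules by current dose.**

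| Current dose | Section 7.4.2 | Table GPGI.3 and footnote b | Values common to both |
|---|---|---|---|
| 20 U or more | 2 to 4 U | 2 to 4 U | all |
| Below 20 U | 2 to 4 U | 1 to 2 U | 2 U only |

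At 20 U or more there is no conflict. Below 20 U, the table's 1 U lies outside 7.4.2, and 3 or 4 U lies outside the table. The excess over the table's maximum is 2 − 2 = 0, 3 − 2 = 1 or 4 − 2 = 2 U.

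**Step 2. Can a trial patient be below 20 U?**

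*At entry.* Inclusion criterion [3] requires "stable doses of once-daily insulin glargine (>0.25 U/kg/day or >20 U/day", so either limb is enough. The weight-based limb alone admits doses under 20 U when body weight is below 20 / 0.25 = 80 kg. Criterion [6] reads "Have body mass index (BMI) ≥23 kg/m² at Visit 1". At BMI 23, 80 kg corresponds to a height of √(80/23) = 1.865 m, so shorter patients can weigh less than 80 kg and still qualify. Examples at BMI 23 (heights assumed; the entry dose must exceed the 0.25 U/kg figure):

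| Height | Weight = 23 × height² | 0.25 U/kg | After a 20% cut |
|---|---|---|---|
| 1.60 m | 58.9 kg | 14.7 U | 11.8 U |
| 1.70 m | 66.5 kg | 16.6 U | 13.3 U |
| 1.80 m | 74.5 kg | 18.6 U | 14.9 U |

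*After randomization.* For baseline HbA1c of 8.0% or less, Section 5.1 states that "the insulin glargine dose will be decreased by 20% immediately after randomization". Since 0.8 × 25 = 20.0, any dose under 25 U falls below 20 U: 0.8 × 24 = 19.2 U and 0.8 × 21 = 16.8 U.

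*By the algorithm itself.* A permitted decrease can cross the threshold, for example 22 − 4 = 18 U.

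The plan expects low doses: the table has a column for them, and 7.4.2 goes on to cover hypoglycemia "In the case of repeated hypoglycemic events, even with a very low glargine dose and despite glargine dose decreases per the TTT algorithm".

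**Step 3. Size relative to dose.** Share = decrease / current dose, at illustrative doses:

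| Current dose | Table: 1 to 2 U | Section 7.4.2: 2 to 4 U |
|---|---|---|
| 12 U | 8.3 to 16.7% | 16.7 to 33.3% |
| 15 U | 6.7 to 13.3% | 13.3 to 26.7% |
| 19.2 U | 5.2 to 10.4% | 10.4 to 20.8% |

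Below 20 U, the 7.4.2 range is twice the table's at both ends. These rows show scale at chosen doses; they say nothing about frequency.

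**The case against.** The strongest reply is that the text largely resolves itself. Section 7.4.2 names the TTT algorithm in the same sentence, Section 5.1 does too, and Section 7.1.3 says the table's criteria apply after hypoglycemia. On that reading there is one rule, which 7.4.2 restates incompletely, and a 2 U cut always satisfies both texts. This settles which text governs. It does not correct the printed range, which still includes 3 and 4 U and omits 1 U for doses below 20 U.

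The triggers are also not word-for-word identical. Section 7.4.2 adds a judgment that the risk is treatment-related and takes the median over the assessment period, where the table uses the last three values. The episode-based triggers match, and these differences do not explain a different dose range.

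The practical points carry more weight. Under Section 7.1.3, patients self-adjust from diaries and training materials that are not among the documents, so the figure they actually work from is unknown. Site staff verify adjustments at each office or telephone visit. Section 7.4.2 itself allows glargine to be stopped for repeated events at a very low dose, so a reduction 2 U too large is modest by comparison. It can also be reversed: during titration the weekly assessment raises the dose once median fasting glucose exceeds 100 mg/dL. During stabilization, increases are limited to severe hyperglycemia, so reversal could wait until Week 4. All of this limits the consequence; none of it makes the two sections agree.

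**Conclusion.** The inconsistency is real: as printed, Section 7.4.2 does not match its own cited algorithm for doses below 20 U. Confidence is high on the textual mismatch and does not extend to any clinical effect. The excess is 0 to 2 U per adjustment, only below 20 U, and toward less insulin after hypoglycemia, so no added hypoglycemia risk is claimed. A deviation requires a patient below 20 U, a reduction trigger, and a site applying 7.4.2 literally with 3 or 4 U. The documents do not give the number of such patients. Change in daily glargine dose is a secondary endpoint without type 1 error control, but no bias in it is shown. Nor is any effect shown on the primary analysis, power or type 1 error. The point is of low severity but worth correcting, because the text instructs insulin dosing.

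**What to change.** Amend Section 7.4.2 so that the glargine decrease follows Table GPGI.3, with both ranges printed: 1 to 2 U if the current dose is below 20 U, and 2 to 4 U if it is 20 U or more. Confirm that the patient diary and site training materials carry the same two ranges. The cost is a one-line protocol clarification or a site memo. No analysis, sample size or SAP text changes.
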